Primary objectives	
UG3 Aims Transitional milestones (24 months study)
 
 • Systematically adapt IMARA for South African 15-19 year old adolescent girls and young women (AGYW) and their Female Caregivers (FC). This will be based upon completed theatre group testing with 48 AGYW-FC dyads. • To conduct pilot testing with approximately 50 AGYW-FC dyads with follow up at 6- and 12-months, in order to establish processes and feasibility for phase II RCT. Key milestones for this phase of the study include obtaining participant STI incidence > 20% (with 100% receiving DOT), uptake of HTC > 70%, uptake of PrEP prescription > 50% and retention at 6 months of > 80%. 
UH3 Aims (36 months)
 
 • Conduct a methodologically-rigorous 2-arm RCT comparing the impact of FUEL-SA and IMARA-SA on 525 15-19 year-old SA-AGYW and their FC on STI and HIV incidence, HTC and PrEP uptake, sexual risk behaviours, and important theoretical mediators. Compared to FUEL-SA, we expect SA-AGYW in IMARA-SA to report increased condom use, have fewer incident STI and HIV infections, be more likely to adopt PrEP and HTC, and demonstrate greater improvement on theoretical mediators of risk at 6- and 12-month follow up. • Evaluate the costs and cost-effectiveness of IMARA-SA compared to FUEL-SA with respect to the acquisition of STI, and where possible, HIV considering power limitations. • Explore participant views and beliefs about PrEP and HTC for SA-AGYW. We will conduct 40 key informant interviews with SA-AGYW and FC about PrEP and explore facilitators and barriers.
Design	The study uses mixed methods which aim to address the study objectives, with qualitative and more participatory methods during the adaptation of the study curriculum, and understanding participant views and beliefs about PrEP. The study also utilizes RCT methods to evaluate family based scalable interventions to prevent HIV and STIs among AGYW aged 15-19 years old.
Study site	Recruitment will occur in Klipfontein/Mitchells Plain (K/MP) health subdistrict and neighbouring areas including crossroads, Philippi, Gugulethu, and from our Tutu

IMARA-1 Study Protocol

Protocol Title: Multilevel Comprehensive HIV Prevention Package for South African Adolescent Girls and Young Women

Protocol PI: [name]

Version 5.0: 14 May 2020

Approved 10JUN2019

Amendment approved xx-xxx-xxxx

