a) Aim 2: Pilot testing with ~50 AGYW-FC dyads (~100 total participants) to establish acceptability and feasibility in preparation for the RCT in phase 2
Recruitment, enrolment and procedures for AIM 2

We will pilot test the revised IMARA curriculum with ~50 new AGYW-FC dyads, using the same eligibility and recruitment procedures described above. Groups will include approximately 6-8 dyads and participants will be followed for 12 months. The procedures for aim 2 are described next:

- We will schedule 8-10 dyads in each cohort to comprise one group. Upon arrival at the research site (Philippi village), trained staff will review consent and assent documents, ensuring comprehension and evaluating if participants are willing to participate.
- Following the consent/assent process, all AGYW and FC will complete a baseline assessment via computer-assisted self-interview (approx. 1 ½ hours) and indicate their desire to test for HIV and STIs and willingness to take PrEP. If willing to test for HIV and STIs, both AGYW and their FC will receive HIV/STI counselling and testing. AGYW and FC have the option to refuse testing and still remain in the study.
- Randomization (control vs. intervention): We will randomize participants to treatment arm upon completion of the baseline assessment so as not to lose families due to bias in advance. Approximately 25 dyads will be randomly assigned to the health promotion group and ~25 dyads to IMARA. Randomization will follow the fish-bowl method, where equal numbers of RED and WHITE cards will be placed in the fish bowl. AGYW will select a card. The two intervention groups will take place in different rooms. The control and IMARA curricula are matched for time and attention.
- The first group session (approx. 3 hours) will be delivered immediately following randomization. Participants will be at site for 6.5 hours for their first session activities, including the baseline assessment and intervention.
- Participants will return one week later for day 2 of the intervention.
- The total time of the intervention is approximately 12 hours.
- Participants who agreed to test for HIV will be given their results at the end of day 1. If HIV positive, referral for care in the regular public ART clinics will be provided. For those who agreed to test for STIs, results will be ready by session 2. If positive, the DTHF nurse will provide STI risk reduction counselling and treatment. We will request the partner be treated as well.

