- For participants who are HIV negative and opt to take PrEP in our baseline survey, we will provide a one month PrEP prescription with a referral to public, youth friendly clinics currently offering PrEP. We will draw blood for safety monitoring of creatinine in

IMARA-1 Study Protocol

Protocol Title: Multilevel Comprehensive HIV Prevention Package for South African Adolescent Girls and Young Women

Protocol PI: [name]

Version 5.0: 14 May 2020

Approved 10JUN2019

Amendment approved xx-xxx-xxxx

accordance with the national guidelines. We will additionally test blood draws for Hepatitis B, in line with national guidelines, among participants who opt to take PrEP at the 6- and 12-month follow-up points. Urine will be tested for pregnancy. Renal function (e.g., creatinine clearance, CrCl) will be tested and all results will be supervised by a medical member of our team. Participants will receive the results with referral documents for the next dose of PrEP.

- At each follow up data collection point and after the second session, we will re-invite individuals for HIV and STI testing. We will also re-invite participants to receive PrEP, unless they accepted PrEP from us at a previous data collection timepoint, were linked to care, and are receiving PrEP from a clinic. Should they be willing to test and to use PrEP, the same procedures as above will apply. At the end of their first month post PrEP initiation and referral, the team will follow up on PrEP and ART uptake at clinics including where they plan to seek PrEP or ART services. We will also ask about whether side effects participants are experiencing when they come for their second visit a week after the first session. We encourage all our participants to contact us should they experience any side effects once they have started using PrEP. During follow-up visits at 6- and 12- months, we will additionally use dried blood spots (DBS) to assess adherence to PrEP among those who have accepted PrEP.
- We will implement extensive retention and tracking procedures (see retention and tracking procedures section below).
- We will re-interview AGYW and FC 6- and 12-months after baseline for preliminary evidence of feasibility and acceptability, particularly with regard to the procedures for HTC, STI and PrEP uptake, and linkage to care for treatment.

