- We will collect written and verbal feedback from participants at the end of each session. Investigators will meet and discuss final proposed changes which will be incorporated into study procedures and the curriculum.
- We will prepare for the RCT and submit an application to Ethics for phase 2 of the study.

The transition from phase 1 to phase 2 of the study is based on meeting specific milestones achieved in the both aim 1 and aim 2 of phase 1.

Procedures for PrEP

Formulation

Young women who are willing to use PrEP in the pilot will be immediately provided a one month supply of a **TENVIR-EM** fixed dose combination tablet containing 200mg emtricitabine and 300mg tenofovir disoproxil fumarate (TDF). **TENVIR-EM** is manufactured by CiplaMed. **TENVIR-EM** has been approved by the US Food and Drug Administration (FDA) for treatment of HIV-1 infection and PrEP to reduce the risk of sexually acquired HIV-1 in adults.

Storage

TENVIR-EM will be stored as per WHO good pharmacy practice (GPP) and good distribution practice (GDP). The tablets will be stored in their original containers on shelves in secure rooms in FPD offices in the study communities. The rooms will only be accessible to authorized study staff. The temperature in the rooms will be controlled by air conditioning between 15°C

IMARA-1 Study Protocol

Protocol Title: Multilevel Comprehensive HIV Prevention Package for South African Adolescent Girls and Young Women
Protocol PI: [name]

Version 5.0: 14 May 2020

Approved 10JUN2019

Amendment approved xx-xxx-xxxx

and 30°C. Room temperature will be monitored twice daily and readings will be documented on a temperature control log. Expiry dates of medication will be monitored monthly. Any problems encountered with stored medication will be reported to the study pharmacist ([name]) who will provide guidance on appropriate resolution steps.

PrEP initiation, dosage and adherence

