
Survey questions added for 6 and 12-month surveys (see Appendix 1): We will ask a set of questions about the COVID-19 virus at 6 and 12 months. These measures will assess the extent to which the outbreak has impacted participants' lives and behaviors, including their sexual behavior, alcohol and drug use, and access to clinical care. Questions will also explore what participants have done to cope with COVID-19. Questionnaire items were adapted from the COVID-19 Exposure and Family Impact Survey,²³¹ the COVID-19 Questionnaire-Child Self-Report Primary version from the Environmental Influences on Child Health Outcomes (ECHO),²³² the CoRonaviruS Health Impact Survey (CRISIS),²³³ and the iTech/ATN survey.

Biological Specimen collection, handling and testing

Biological specimen collection. We have carefully considered availability of procedures for age-appropriate biologically verified HIV and STIs. We have sought out the latest available but least invasive methods based on preparatory research of available test kits, assays, lab space, and pricing. As such, we have chosen finger prick HIV tests and urine tests for STIs (chlamydia, gonorrhea, trichomonas). We will use trained and certified counsellors, clinic and lab teams to gather HIV/STI biological data and to conduct referrals for confirmatory testing and treatment. For participants interested in PrEP, our staff are also trained to draw blood, conduct creatinine assessments, and test for Hepatitis B and DBS samples for PrEP adherence. These specimens will be used to monitor STI incidence > 20% (with 100% receiving DOT), uptake of HTC > 70%, uptake of PrEP prescription > 50% and retention at 6 months of > 80%. While HIV tests will be done at site, urine and blood specimens will be sent to BARC for testing. We will offer AGYW PrEP at each assessment, unless the participant has accepted PrEP from us during a previous data collection timepoint, been linked to care, and is receiving PrEP from a clinic.

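### Does the phase 2 milestone for PrEP prescription above 50% fail because its denominator and time point are not stated?

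*Combined protocol and SAP*

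**What the plan says.** The milestones appear in the Protocol Summary (Primary objectives) and again under Biological Specimen collection, handling and testing: "uptake of HTC > 70%, uptake of PrEP prescription > 50% and retention at 6 months of > 80" per cent. The end of the Aim 2 procedures gives them their role: "The transition from phase 1 to phase 2 of the study is based on meeting specific milestones" reached in the two aims of phase 1.

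The Aim 2 procedures describe how a participant reaches a prescription. At the baseline assessment, before the card is drawn, participants "indicate their desire to test for HIV and STIs and willingness to take PrEP". Testing is voluntary: "AGYW and FC have the option to refuse testing and still remain in the study". The prescription itself is conditional: "For participants who are HIV negative and opt to take PrEP in our baseline survey, we will provide a one month PrEP prescription". Later offers are planned after session 2 and at each follow-up: "We will also re-invite participants to receive PrEP, unless they accepted PrEP from us at a previous data collection timepoint" and are already receiving it from a clinic. Section 3 (Human Subjects Protection) allows HIV-infected AGYW and female caregivers (FC) to enrol.

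On who is offered PrEP, the formulation paragraph speaks of "Young women who are willing to use PrEP in the pilot", and the sentence on the PrEP offer that follows the milestones in the specimen section names AGYW. Data Collection Procedures and the later HTC paragraph include FC. Data Reduction and Analyses builds the PrEP and HTC uptake summary scores for AGYW.

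**The concern.** A go/no-go criterion should give one answer from one data set. This one names an event (a prescription) and a threshold (50%) but not who is counted or by when. Those who decline testing and those who are HIV positive cannot reach the event under the Aim 2 wording, so the choice between all enrolled and tested negatives matters. On the all-enrolled base, PrEP uptake is capped by HTC uptake times the HIV-negative share, so the two milestones are linked. Counting AGYW alone or AGYW with FC, and counting baseline prescriptions or prescriptions to date, can also change the figure. If the base were picked after the uptake data were seen, the move to a trial of 525 dyads could rest on that choice.

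**Working it through.** **Inputs from the documents.** HTC above 70%; PrEP prescription above 50%; about 50 dyads, so about 50 AGYW or 100 participants. **Inputs not in the documents, assumed:** HIV prevalence among testers p (0%, 10%, 20%) and acceptance among tested negatives a (60% for illustration). The plan gives no derivation of the 50% threshold, so there is no figure to reproduce.

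**Required acceptance.** With HTC uptake h and all enrolled as the base, the criterion needs a > 0.50 / (h × (1 − p)). With tested negatives as the base it needs a > 0.50 whatever h and p are.

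| HTC uptake h | p = 0% | p = 10% | p = 20% |
|---|---|---|---|
| 70% | 71.4% | 79.4% | 89.3% |
| 80% | 62.5% | 69.4% | 78.1% |
| 90% | 55.6% | 61.7% | 69.4% |
| 100% | 50.0% | 55.6% | 62.5% |

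The two bases disagree when acceptance lies between 50% and the table entry. With no HIV infection that band is 21 points wide at 70% HTC and under 6 points at 90%.

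**Whole persons.** Exactly 70% testing misses a milestone of more than 70%, so the lowest qualifying case is 71 of 100. With no HIV infection, the all-enrolled base then needs 51/71 = 71.8% and the tested base 36/71 = 50.7%. For 50 AGYW with 36 tested, the figures are 26/36 = 72.2% and 19/36 = 52.8%.

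**Chance that the PrEP criterion is met at a = 60%** (binomial upper tail):

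| Enrolled | Tested negative | Tested-negative base | All-enrolled base |
|---|---|---|---|
| 100 | 71 (71% HTC, p = 0) | 36 needed: 96% | 51 needed: 3% |
| 100 | 63 (70% HTC, p = 10%) | 32 needed: 95% | 51 needed: 0.03% |
| 100 | 90 (90% HTC, p = 0) | 46 needed: 97% | 51 needed: 78% |
| 100 | 81 (90% HTC, p = 10%) | 41 needed: 97% | 51 needed: 34% |
| 50 AGYW | 36 (72% HTC, p = 0) | 19 needed: 85% | 26 needed: 9% |
| 50 AGYW | 45 (90% HTC, p = 0) | 23 needed: 91% | 26 needed: 68% |

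The rows for 100 treat the two members of a dyad as independent. Correlation within dyads would soften the extreme values. The AGYW rows do not have this problem, because one girl per family is enrolled.

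**Population and time.** With assumed acceptance of 60% in AGYW and 35% in FC (equal numbers), AGYW alone gives 60% and the pair gives (60 + 35)/2 = 47.5%. With an assumed 40% at baseline and 20% of decliners accepting later, baseline uptake is 40% and uptake to date is 40 + 0.20 × 60 = 52%. Both illustrations straddle 50%, but only because the assumed rates do.

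**Precision.** With 36 tested AGYW and 60% acceptance, the 95% half-width is 1.96 × √(0.6 × 0.4/36) = 0.16, or 16 points. On any base, a pilot of this size gives a rough reading of the criterion.

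**The case for a change.** The strongest case for a change is that the milestones govern the move to phase 2, so their definition matters more than any arm comparison in the pilot. The headline figure of 71% uses only the plan's own 70% and 50% and is the most lenient value at that testing level. The remedy would be one sentence. All of that is true, and the missing base and date are a real gap.

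Several things limit its weight. The contrast is most extreme at the HTC floor and shrinks as testing rises; repeat invitations after session 2 and at follow-up can raise cumulative HTC. The population is less open than it seems, since the PrEP offer beside the milestones and the uptake summary scores both refer to AGYW, and offering FC a service does not put them in the criterion. The and/or wording in Data Collection Procedures governs referral to a medical officer, while the Aim 2 wording governs the prescription, so the two can stand together. The plan does not say that one missed milestone stops phase 2. The milestones also belong to the UG3/UH3 funding programme, and the documents do not show whether they are defined further there. It therefore cannot be said that the base is free to be chosen after the data are seen, though the protocol alone does not exclude it.

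**Conclusion.** No change to the plan follows. The protocol leaves out a definition, but no stated threshold, rule or analysis is shown to be wrong. Either base answers a sensible question: prescriptions among all enrolled measure reach, and prescriptions among tested negatives measure acceptance. The numbers enrolled, tested, HIV negative and prescribed all arise from the planned procedures, so a competent report can show both ratios, for AGYW and FC separately and by visit, without collecting anything more. Only retention is dated, at 6 months, and that is a natural point at which to read the set; this is my inference, not the protocol's.

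The choice of base moves the required acceptance from 50% to about 71% at 70% HTC, and to about 56% at 90% HTC, both with no HIV infection. Any HIV infection among testers raises the all-enrolled figures, to 79% and 62% at an assumed 10%. These results rest on reading the Aim 2 procedures to mean that only tested, HIV-negative participants receive a prescription, and on prevalence and acceptance values that the documents do not give. I take no view on who should be offered PrEP.

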	teen mobile unit. Participants will be invited to come to the Desmond Tutu HIV Foundation satellite research site in Philippi village for consent procedures, medical study components and group sessions.
Study drugs	Oral Pre-exposure prophylaxis (Truvada) (one month supply); STI treatment: N. gonorrhoea – Ceftriaxone 250 mg injection (Rocephin®) AND Azithromycin (Zithromax™) 1g orally; C. trachomatis – Azithromycin (Zithromax™) 1g orally; T. vaginalis – Metronidazole (Flagyl™) 2g orally; HIV testing and counseling (HTC)
Study population	15 – 19-year-olds, AGYW and their Female Caregivers (24 years and older)
Sample size	A total of ~1250 participants are expected to be enrolled across all study components as follows: 
 1. Up to 96 participants in aim 1 theatre testing component 2. Up to 100 participants in the pilot study 3. Up to 1050 participants in the RCT 4. Up to 40 participants in the qualitative component
Treatment regimen	Referral to ART clinics for HIV positive participants; Referral for PrEP for HIV negative participants with a one month supply provided at enrolment if participants are willing to take PrEP.
Study duration	5 years (2 years UG3 feasibility) and (3 years UH3 RCT)
Duration of enrolment and accrual	36 months
Primary endpoints	An adapted and tailored SA IMARA curriculum; Impact of IMARA on HIV and STI incidences; PrEP uptake; HTC uptake; Cost effectiveness and scalability of IMARA; Sexual risk behaviour (condom use, number of partners)
Key secondary endpoints	AGYW-FC relationship (warmth, acceptance, monitoring, permissiveness); AGYW-FC communication (quality, frequency); HIV knowledge (HIV/STI transmission, prevention); HIV-related Stigma; HIV and STI attitudes; AGYW mental health (depression, anxiety, trauma); AGYW and FC knowledge, attitudes and beliefs about PrEP and HTC; Adherence (PrEP and ART); Gender roles and gender-based violence; Drug use; Partner communication; and Power relationship dynamics.

IMARA-1 Study Protocol

Protocol Title: Multilevel Comprehensive HIV Prevention Package for South African Adolescent Girls and Young Women

Protocol PI: [name]

Version 5.0: 14 May 2020

Approved 10JUN2019

Amendment approved xx-xxx-xxxx

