STI. At each assessment, we will collect urine to screen for *N. gonorrhoeae*, *C. trachomatis*, and *T. vaginalis*. We will give participants collection containers and escort them to a private, secure room in which to produce the specimen. Staff will decant the urine to centrifuge tubes labelled with unique, anonymous, subject-sample identifiers and store them in refrigerators. The BARC laboratory will use nucleic acid amplification technologies (NAAT) for STI testing^{234, 235} and email the results using a password protected server to us within one week. AGYW who test positive for an STI will be offered free single-session directly observed therapy by our Clinical nurse practitioner (CNP) and a medical officer on site with the following antimicrobials: *N. gonorrhoea* – Ceftriaxone 250 mg injection (Rocephin®); *C. trachomatis* – Azithromycin (Zithromax™); All HTC procedures will comply with the DTHF standard operating procedures.

Our staff and counsellors at our site are extensively trained and highly experienced conducting HTC with youth and adults. At baseline, HTC will be conducted following the workshop so as not to interfere with the day's activities. At follow-up, HTC will occur at the end of the assessments so as not to interfere with other survey materials. Urine samples will be sent to the BARC laboratory for testing and an HIV rapid test will be conducted. AGYW who test positive for HIV will be immediately linked to care at ART public clinics and an appointment for follow-up care will be arranged. The project coordinator working closely with the CNP nurse will track appointment attendance by reaching out to our referral clinics. An SOP is already in place where PrEP uptake data is obtained from these clinics and we will work with the existing

SOP to obtain our participants PrEP uptake information. For STI and HIV results, we will maintain subject-sample ID linkages in confidential logs kept in secure, locked storage. The DTHF has been using these procedures for many years with no adverse events. We will offer Pre-Exposure Prophylaxis (PrEP) to AGYW and FC at each assessment point. For interested participants, we will schedule an appointment at the DTHF clinic and assist with transportation or attendance, as needed, to the initial appointment

Data reduction, data analysis and expected outcomes

Expected outcomes

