3.2. Risk/Benefits to participants

Benefits/risks to participants: We anticipate that this study will provide immediate benefits to the participants through participating in sessions, testing for HIV/STIs and receiving treatment. Participants will also benefit by being offered PrEP hence preventing HIV infection.

Potential Risks.

This research includes a number of potential risks which we outline below. We detail procedures to minimize these risks.

- Biological specimen collection.** We have carefully considered availability of procedures for age-appropriate biologically verified HIV and STIs. We have sought out the latest available but least invasive methods based on preparatory research of available test kits, assays, lab space, and pricing. Our team is well trained to handle all testing procedures and complete referrals where necessary.
- Interested AGYW and FC will provide urine for STI testing, saliva/finger prick for HIV testing, and blood draws for PrEP at all three time points. AGYW and FC who take up PrEP will also be invited to provide a dried blood spot to test for adherence to PrEP at

follow-up visits. Consistent with our previous studies, we will provide participants with urine collection containers and escort them to a private, secure room in which to produce the specimen. We will train staff to use proper procedures to obtain urine from subjects and approved procedures for the safe handling of urine. Staff will decant the urine to centrifuge tubes labeled with unique, anonymous, subject-sample identifiers and store the specimens in refrigerators. We will send our samples to BARC laboratory will use nucleic acid amplification technologies (NAAT) for STI testing and email the results using a password protected server to study staff in the US within one week. AGYW and FC who test positive for an STI will be referred to our DTHF Medical Officers for treatment. We will adhere to all DTHF standard operating procedures for management of STIs and will at minimum include a free single-session directly observed therapy with the following antimicrobials, each of which constitutes a single session therapeutic regimen: N. gonorrhoea – Ceftriaxone 250 mg injection (Rocephin®) AND Azithromycin (Zithromax™) 1g orally; C. trachomatis – Azithromycin (Zithromax™) 1g orally; T. vaginalis – Metronidazole (Flagyl™) 2g orally HIV testing and counseling (HTC) will be conducted by DTHF trained and certified staff at the clinical research sites

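### The specimen section's gonorrhoea regimen falls below the protocol's own minimum, and one PrEP supply sentence omits the HIV-negative condition

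*Combined protocol and SAP*

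**What the plan says.** **STI treatment.** The regimen appears in three places.

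- Biological Specimen collection, handling and testing, STI paragraph: "AGYW who test positive for an STI will be offered free single-session directly observed therapy". The drug list that follows reads "Ceftriaxone 250 mg injection (Rocephin®); *C. trachomatis* – Azithromycin (Zithromax™); All HTC procedures will comply".
- Section 3.2, Risk/Benefits to participants: management "will at minimum include a free single-session directly observed therapy", and the drugs are "N. gonorrhoea – Ceftriaxone 250 mg injection (Rocephin®) AND Azithromycin (Zithromax™) 1g orally; C. trachomatis – Azithromycin (Zithromax™) 1g orally". Metronidazole 2 g for T. vaginalis follows. On who is treated: "AGYW and FC who test positive for an STI will be referred to our DTHF Medical Officers for treatment".
- Protocol Summary, Study drugs: for N. gonorrhoea, "Ceftriaxone 250 mg injection (Rocephin®) AND Azithromycin (Zithromax™) 1g orally".

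**PrEP supply.** The Treatment regimen row of the Protocol Summary and the Aim 2 pilot procedures both reserve the one-month supply or prescription for participants who are HIV negative and want it. The Formulation paragraph under Procedures for PrEP says that willing young women get a one-month supply immediately. It says nothing about HIV status.

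**Context.** The Aim 2 procedures let adolescent girls and young women (AGYW) and female caregivers (FC) decline testing and stay in the study. They release HIV results at the end of day 1. Section 3 admits both HIV-infected and uninfected participants.

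**The concern.** Section 3.2 sets a floor, and the specimen section's gonorrhoea entry lies below it. The specimen section does not cross-refer to section 3.2 or say which list prevails. Its sentence on standard operating procedures covers HIV testing and counselling, not STI treatment. Someone working from that section could give one drug where the protocol requires two.

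On PrEP, eligibility to start depends on HIV status, and this population is not screened to be HIV negative. Willingness is recorded at the baseline assessment, before the test result exists. A sentence that ties immediate supply to willingness alone does not say that the result must come first.

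What is at stake is consistent treatment of participants and a single standard to monitor against. Section 3 describes phase 1 as piloting the procedures to be used in the phase 2 trial of 525 dyads, so uncorrected text could be carried forward.

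**Working it through.** No sample size, power or event figure is involved, so there is nothing to recompute. The check compares the texts side by side.

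**Step 1. Gonorrhoea regimen**

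| Place | Ceftriaxone | Azithromycin |
|---|---|---|
| Protocol Summary, Study drugs | 250 mg | 1 g |
| Section 3.2 (stated as a minimum) | 250 mg | 1 g |
| Biological Specimen section, STI paragraph | 250 mg | not listed |

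The minimum has 2 drugs and the specimen section lists 1, so 2 − 1 = 1 is missing. This conflict is internal to the protocol and needs no outside guideline.

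**Step 2. Could the missing drug be lost text?** The gonorrhoea entry closes with a semicolon straight after the ceftriaxone brand name, and the chlamydia entry follows. There is no redaction or missing-figure marker. Loss in the middle of a list is possible but unlikely. The end of the list is different: it stops at a semicolon and runs into the HIV testing sentence. The absent T. vaginalis entry may therefore be lost text and is not counted.

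**Step 3. PrEP supply condition**

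| Place | Willing | HIV negative |
|---|---|---|
| Protocol Summary, Treatment regimen | yes | yes |
| Aim 2 pilot procedures | yes | yes |
| Procedures for PrEP, Formulation | yes | not stated |

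The paragraph on PrEP initiation, dosage and adherence assigns initiation to a medical officer or clinical nurse practitioner. It does not state the HIV-negative condition either.

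**Step 4. Does the order of events make the omission matter?** On day 1:

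1. Consent, then the baseline assessment, where willingness to take PrEP is recorded (Aim 2 procedures).
2. Randomisation and the first group session (Aim 2 procedures).
3. HIV testing, after the workshop (Biological Specimen section).
4. HIV results, at the end of the day (Aim 2 procedures).

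Willingness at step 1 comes before the result at step 4. A participant who declines testing has no result at all. Read by itself, the Formulation sentence could be satisfied before HIV status is known.

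**The case against.** The strongest reply is that the governing rules are already present and correct. Section 3.2's floor applies whatever a shorter list says, and that section also binds STI management to the site's standard operating procedures. The Formulation sentence mainly identifies the product. It follows the stepwise Aim 2 procedure, which states the HIV-negative condition and applies the same procedures at follow-up. A clinician starts PrEP, and the referral clinics that supply it later are described as serving HIV-negative users. All of this stands and keeps the point minor. It does not remove the disagreement between sentences of one protocol version.

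Several stronger readings are tempting but are not supported:

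- *The study plans to dispense PrEP without a test.* The Protocol Summary and the Aim 2 procedures say otherwise.
- *Data Collection Procedures makes HIV-negative status optional for PrEP by joining it to desire for PrEP with and/or.* That sentence governs referral to a medical officer, not supply. Tightening it could keep an untested participant who wants PrEP from reaching the person who could discuss testing.
- *Caregivers go untreated.* The specimen section names only AGYW but does not exclude FC. The Aim 2 procedures state that "both AGYW and their FC will receive HIV/STI counselling and testing" for those willing to test, and then "If positive, the DTHF nurse will provide STI risk reduction counselling and treatment". Data Collection Procedures covers every participant who tests positive, and section 3.2 names FC.
- *Chlamydia has no defined dose.* The specimen section omits it, but the Protocol Summary and section 3.2 both give 1 g and nothing contradicts them.

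**Conclusion.** The point holds in two places. The specimen section's gonorrhoea entry lacks one of the two drugs that section 3.2 requires as a minimum. The Formulation sentence lacks the HIV-negative condition that the Protocol Summary and the Aim 2 procedures set. Both are wrong as written, and both are minor because correct text and clinician involvement exist elsewhere.

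A reader might go on to infer that under-treated gonorrhoea would raise repeat positive tests and so affect the STI incidence milestone. The documents give no cure rates and do not show that staff would follow the shorter list, so no effect on incidence, milestones or any estimate is claimed.

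The STI part assumes that the mid-list omission of azithromycin is in the source and did not arise when the text was extracted. A look at the original page would settle that.

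**What to change.** 1. **Biological Specimen section, STI paragraph.** Replace the drug list with the section 3.2 regimen: for N. gonorrhoea, ceftriaxone 250 mg by injection plus oral azithromycin 1 g; for C. trachomatis, oral azithromycin 1 g; for T. vaginalis, oral metronidazole 2 g. As a conforming edit, name both AGYW and FC as those offered treatment.
2. **Procedures for PrEP, Formulation.** Reword along these lines: *participants with a negative HIV test who wish to use PrEP in the pilot receive one month's supply after that result is known*. Participants should replace young women because Data Collection Procedures and the specimen section include FC in the PrEP offer.
3. **Data Collection Procedures.** Leave the referral sentence as it is. The HIV-negative condition belongs at supply.

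The cost is a wording amendment in two places, plus any site procedure text copied from them. No procedures, visits or participants are added.
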